If the participant prematurely discontinues from the trial, this will be their last study visit, unless there is an ongoing adverse event that will continue to be monitored until resolution or until the Investigator and Medical Monitor determine that no additional follow-up is medically necessary.

Otherwise, the participant will return to the study site for the final 3-month, LTFU, visit.

7.1.9 3-Month Long-Term Follow-up (LTFU) Visit

Approximately three months (i.e., 90 days) after Study Day 1, participants will return for the final, 3-month, Long-Term Follow-up (LTFU) visit. At this visit, a number of protocol-mandated tests, examinations, assessments and procedures will be done as described below.

- Inquire about any changes in the participant's health in a non-suggestive manner; however, any changes noted will not be considered adverse events unless they either were noted prior to the Study Day 30 / EoT visit and/or are considered to be 'possibly' or 'probably' related to study drug administration.
- Review concomitant medications/therapies (including psychotherapy and healthcare utilization).
- Perform a brief physical exam and obtain weight (only if Study Day 8 visit was not completed).

CONFIDENTIAL

- Obtain vital sign measurements.
- Obtain urine samples for:
 - Qualitative rapid urine drug screen.
 - Qualitative urine ethyl glucuronide (EtG) test to assess alcohol consumption.
- Review participant's use of health tracking wearable device and collect the device and download the data to the trial database.
- Administer and/or have the participant complete the following clinician rating scales and participant QoL and PRO instruments, respectively:
 - GAD-7
 - PHQ-9
 - BPI
 - NIH HEALS
 - C-SSRS
 - AUDIT
 - DUDIT

Upon completion of the 3-month, long-term follow-up visit and after the study site staff obtain all outstanding data, participants will have completed the study, except if there is an ongoing adverse event that the Investigator and/or Medical Monitor believe warrants continued monitoring until resolution or until it is determined that no additional follow-up is medically necessary.

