10. ADVERSE EVENTS

An AE is defined as any untoward or unfavorable medical occurrence in a clinical research study that is observed, measured or reported by a participant, including any abnormal sign (e.g., abnormal physical exam or laboratory finding), symptom or disease, temporally associated with the participants' involvement in the research, whether or not considered related to participation in the research. This definition includes concurrent illnesses or injuries and exacerbation of pre-existing conditions.

An unexpected AE is one that is not listed in the current Investigator's Brochure or an event that is by nature more specific or more severe than a listed event.

All AEs will be monitored by the Investigator or site staff until resolution or, if the AE becomes chronic, a cause identified. If an AE is unresolved at the conclusion of the study, a clinical assessment will be made by the Investigator and/or Medical Monitor as to whether continued

follow-up of the AE is warranted.

All adverse events will be recorded in the participant's medical record and in the AE form of the eCRF.

The severity of events will be determined by the Investigator as:

- Mild: no limitation in normal daily activity
- Moderate: some limitation in normal daily activity
- Severe: unable to perform normal daily activity

The relationship of the study drug to an AE will be determined by the Investigator, based on the following definitions:

- Not Related

The AE is not related if exposure to the investigational product has not occurred, or the occurrence of the AE is not reasonably related in time, or the AE is considered unlikely to be related to use of the investigational product, ie, there are no facts (evidence) or arguments to suggest a causal relationship, or the AE is more likely related to the participant's pre-existing condition.

- Possibly Related

The administration of the investigational product and the AE are considered reasonably related in time and the AE could be explained by causes other than exposure to the investigational product.

- Probably Related

Exposure to the investigational product and AE are reasonably related in time and the investigational product is more likely than other causes to be responsible for the AE, or is the most likely cause of the AE.

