10.3. Adverse Event Collection

All AE and SAEs will be collected during the entirety of the participant's involvement in the trial. If a new AE/SAE is reported >30 days after Study Day 1 and up until the 3-month, LTFU visit, it will be recorded in the participant's medical record and the eCRF; however, unless the event is deemed to be possibly or probably related to the study drug, it will not be recorded as an adverse event.:

- Events related to planned treatments or physician visits for baseline conditions collected in the medical history will not be collected unless there is an exacerbation of the condition.
- Any AE leading to withdrawal from continued participation in the trial protocol will be collected throughout the study.
- All AEs related to changes in psychiatric status will be collected throughout the study.

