10.4. Serious Adverse Event Reporting

All SAEs which occur during the course of the trial, whether considered to be associated with the study drug or not, must be reported to the Investigator within 24 hours (or at the latest on the following working day) of the any member of the study site staff learning that an event occurred, irrespective of causality.

Contact information for the Medical Monitor and Study Monitor are provided in a separate

CONFIDENTIAL

document.

- SAEs will be assessed by the Investigator and Medical Monitor for relatedness, seriousness, and unexpectedness, and reported to regulatory agencies, IRBs, and the Investigator according to applicable regulations and policies. The Investigator should notify their respective IRBs according to IRB-specific timelines promptly after assessment.
- SAE reporting to competent authorities (e.g. FDA) is to be done by an authorized delegate.

The Investigator is responsible for the overall safety of the participants, the ongoing safety evaluation of the investigational product for providing the required medical expertise in conjunction with site medical personnel to address trial-related medical questions or problems.

The Investigator (and the Medical Monitor) alone (or jointly) will determine if the SAE will require expedited reporting and what follow-up information is needed for evaluation. If no consensus can be reached, the different assessments and the reasons for this must be summarized in writing. In any case, the most conservative assessment will drive the reporting procedure. The time frame for reporting SAEs to regulatory authorities begins when the Investigator has “initial information” of the event regardless of the form that initial notification takes. Expedited timelines will be followed according to regulatory, institutional, and IRB requirements.

The Investigator is responsible for ongoing safety evaluation of the investigational product and for the prompt notification to regulatory authorities of findings that could adversely affect the safety of participants, impact the conduct of the trial, or alter the IRB’s approval/favorable opinion to continue the trial.

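### New events after Day 30 count as adverse events only if judged drug-related, which contradicts the protocol's own AE definition and its unrestricted primary endpoint

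*Protocol*

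**What the plan says.** Section 10.3 opens without restriction: "All AE and SAEs will be collected during the entirety of the participant's involvement in the trial". It then sets a different rule for late events: "If a new AE/SAE is reported >30 days after Study Day 1 and up until the 3-month, LTFU visit", the event goes into the medical record and the eCRF, but unless it is judged possibly or probably related, "it will not be recorded as an adverse event". Two bullets below this say that AEs leading to withdrawal and AEs concerning psychiatric status are collected throughout the study.

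Section 7.1.9 (3-month LTFU visit) repeats the condition in other terms: "any changes noted will not be considered adverse events unless they either were noted prior to the Study Day 30 / EoT visit", or are considered possibly or probably related. The Day 90 text in the synopsis and in Section 4.1 likewise limits AE assessment at that visit to related events and events unresolved at the EoT visit.

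Other sections carry no such limit:
- Section 10 defines an AE "whether or not considered related to participation in the research", sends all AEs to the AE form of the eCRF, and gives the relatedness judgement to the investigator.
- Section 8.1 has AEs and SAEs noted at each study visit.
- Section 10.4 states: "All SAEs which occur during the course of the trial, whether considered to be associated with the study drug or not, must be reported".
- Section 4.4.1 makes the number and incidence of AEs and SAEs the primary endpoint, with no time or relatedness limit.
- Section 12.3 defines TEAEs as AEs that arise or worsen after treatment, again with no such limit.

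**The concern.** The primary endpoint is a count, so the rule for what enters the count has to be single and clear. Here it changes after Day 30 from all-cause to related-only, and the endpoint and TEAE definitions do not say so. A reader of the final tables would take them as all-cause incidence over the whole of follow-up.

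The judgement that decides entry is made in an open-label, single-arm study, where no comparator shows how often such events occur without the drug. The protocol's own definitions make a late event easy to exclude. Section 10 allows an event to be called not related if it is not reasonably related in time or is more likely due to a pre-existing condition, and Section 2.3.2 gives psilocin a half-life of around 108 minutes with complete excretion within 24 hours. Excluding events can move the count in one direction only: down.

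**Working it through.** The protocol gives no expected event rate and no derivation for its sample size, so there is no stated figure to reproduce. Three checks apply.

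**1. Share of follow-up under the related-only rule**

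Inputs: the LTFU visit falls "Approximately three months (i.e., 90 days) after Study Day 1" (7.1.9), with a window of ±7 days (Table 1); the rule starts after 30 days (10.3); up to 24 participants are treated (12.2).

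- Nominal: (90 − 30)/90 = 60/90 = 66.7%.
- LTFU at 83 days: 53/83 = 63.9%. LTFU at 97 days: 67/97 = 69.1%.
- In participant-days: 24 × 60 = 1,440 of 24 × 90 = 2,160.
- If the cut-off follows the EoT visit instead (Day 30 ± 5, as 7.1.9 implies), with LTFU at 90: from 55/90 = 61.1% to 65/90 = 72.2%.

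**2. How easily an event could drop out of the count**

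The event rates below are assumptions; the document gives none. Let p be the proportion of participants with at least one new event in the late period that is judged unrelated. The expected number affected is 24p, and the chance that at least one participant is affected is 1 − (1 − p)^24.

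| Assumed p | Expected of 24 | Chance of at least one |
|---|---|---|
| 2% | 0.5 | 38% |
| 5% | 1.2 | 71% |
| 10% | 2.4 | 92% |
| 20% | 4.8 | 99.5% |

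**3. The rules side by side**

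- *An unrelated new event on Day 60.* Under Section 10 it is an AE and goes on the AE form. Under 10.3 and 7.1.9 it is not recorded as an AE. Both cannot be applied to the same event.
- *An unrelated SAE on Day 60.* Under 10.4 it is reported. Under 10.3 it is not an AE, so it has no place in the serious-TEAE table of 12.3. The safety reports and the tables would not reconcile.
- *A psychiatric AE on Day 60, judged unrelated.* The 10.3 bullet has it collected throughout, but collecting an event is not the same as recording it as an AE, and 7.1.9 names no exemption. Its status is undetermined, although mental and psychotic AEs are a named component of the primary endpoint.
- *The cut-off.* Section 10.3 goes by the date of report; 7.1.9 goes by whether the event was noted before the EoT visit. Take an event that starts on Day 15 and is first reported at an EoT visit on Day 33, which is within the window. Read literally, 10.3 filters it because it was reported more than 30 days after dosing, although its onset lies well inside the first 30 days.

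**The case against.** Three stronger conclusions might be inferred, and the document does not support them.

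- *That late events vanish, or that incidence to Day 90 can never be stated.* Section 10.3 puts these events in the medical record and the eCRF. They lose AE status, and with it their place in the AE and TEAE tables, but they could still be listed.
- *That 10.3 and 10.4 cannot both be obeyed.* Section 10.4 governs reporting and 10.3 governs classification. Staff can report an unrelated late SAE and still not class it as an AE. Section 10.4 also brings in the medical monitor and lets the most conservative assessment drive reporting if the two disagree. The defect is a failure to reconcile.
- *That two thirds of the primary endpoint is filtered.* The 67% is calendar time. Only new events are affected; those noted before the EoT visit stay AEs. Only one scheduled post-dose visit, Day 90, falls in the period. Table 1 schedules no laboratory tests after Day 30 and no ECG after Day 8, so the rule has no scheduled liver, kidney or ECG finding to remove in that period. Vital signs are still taken at the LTFU visit, so new blood pressure and heart rate findings are exposed.

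It can also be argued that the two-tier window is deliberate. It appears in four places, the study-pause criteria in Section 9.4 also run to Day 30/EoT, and a single dose of a rapidly cleared drug gives it a rationale. That may be so, but a deliberate window belongs in the endpoint and TEAE definitions, and it is in neither. The argument therefore accepts that the text must change.

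**Conclusion.** The contradiction stands. Sections 10.3 and 7.1.9, with the Day 90 text in the synopsis and 4.1, deny AE status to new unrelated events after about Day 30. Section 10, the opening of 10.3, 4.4.1 and 12.3 do not allow for that. The rule covers about 60 of 90 nominal days (64% to 69% across the LTFU window) and, for new events in that time, can only reduce the AE and TEAE counts. With 24 participants, even an assumed 5% rate of new unrelated events gives a 71% chance that at least one participant has an event left out. That figure rests on the assumed rate; the direction of the effect does not.

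The problem concerns classification and counting: the information is kept. Because the protocol itself fixes what is recorded as an AE, a SAP that tabulates AEs as recorded would inherit the restriction.

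**What to change.** Preferred change: in 10.3, 7.1.9, 4.1 and the synopsis, remove the relatedness condition and record every new AE and SAE through the LTFU visit as an AE on the AE form, with relatedness as an attribute. Summarise all-cause and related TEAEs to Day 30 and to Day 90. Section 12.3 already asks for related TEAEs separately, so only the two time windows are added.

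If the sponsor intends a two-tier window, the minimum is:
- state in 4.4.1 and 12.3 that all-cause AEs run to Day 30 and only related events are counted after it;
- use one cut-off, based on onset date, in 10.3 and 7.1.9;
- count all SAEs to the LTFU visit regardless of causality, so that the tables agree with 10.4 reporting;
- say whether psychiatric AEs and AEs leading to withdrawal are exempt from the related-only rule.

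The cost is a few more AE entries at a visit that already exists and a slightly higher reported AE count. No new visit or procedure is needed.

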10.4. Serious Adverse Event Reporting

All SAEs which occur during the course of the trial, whether considered to be associated with the study drug or not, must be reported to the Investigator within 24 hours (or at the latest on the following working day) of the any member of the study site staff learning that an event occurred, irrespective of causality.

Contact information for the Medical Monitor and Study Monitor are provided in a separate

CONFIDENTIAL

document.

- SAEs will be assessed by the Investigator and Medical Monitor for relatedness, seriousness, and unexpectedness, and reported to regulatory agencies, IRBs, and the Investigator according to applicable regulations and policies. The Investigator should notify their respective IRBs according to IRB-specific timelines promptly after assessment.
- SAE reporting to competent authorities (e.g. FDA) is to be done by an authorized delegate.

The Investigator is responsible for the overall safety of the participants, the ongoing safety evaluation of the investigational product for providing the required medical expertise in conjunction with site medical personnel to address trial-related medical questions or problems.

The Investigator (and the Medical Monitor) alone (or jointly) will determine if the SAE will require expedited reporting and what follow-up information is needed for evaluation. If no consensus can be reached, the different assessments and the reasons for this must be summarized in writing. In any case, the most conservative assessment will drive the reporting procedure. The time frame for reporting SAEs to regulatory authorities begins when the Investigator has “initial information” of the event regardless of the form that initial notification takes. Expedited timelines will be followed according to regulatory, institutional, and IRB requirements.

The Investigator is responsible for ongoing safety evaluation of the investigational product and for the prompt notification to regulatory authorities of findings that could adversely affect the safety of participants, impact the conduct of the trial, or alter the IRB’s approval/favorable opinion to continue the trial.

Any employee, contractor, or contract organization working on behalf of the Investigator who discovers a serious adverse experience in the context of a clinical trial is responsible for alerting the study site staff trial staff. The Investigator is responsible for collecting serious adverse experience information and submitting safety reports to regulatory agencies.

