9.4. Criteria for Termination or Suspension of the Study

The study will be fully enrolled and completed as planned unless one or more of the following criteria are satisfied that require temporary suspension of the study.

- New information regarding the safety or efficacy of the study drug indicates a significant change in the known risk/benefit profile for the drug, such that the risk is no longer acceptable for subjects participating in the study.
- Significant violation of Good Clinical Practice (GCP) that compromises the ability to achieve the primary study objectives or compromises subject safety.
- Study-specific criteria for suspension of the study:
 - The study will be paused if:
 - One participant experiences any of the following during the treatment phase of the trial starting at the time of study drug administration and through Study Day 30/ EoT, even if the participant prematurely discontinued further involvement in the trial:
 - A CTCAE Grade 3 – 5 toxicity which is possibly or probably related to study treatment,
 - A suicide attempt,
 - A marked prolongation of QT interval (i.e., $QT \geq 450$ msec) over a series of 3 ECGs performed within 5-6 minutes,
 - A serious episode of psychosis as determined by the Investigator that requires immediate medical attention,
 - A severe, non-serious, AE possibly related to study treatment,
 - Two participants experience: One or more serious AE's possibly or probably related to study treatment.

The study might also be terminated by the sponsor for the following reasons:

- Slow patient enrollment,
- Data collected lacking quality,
- Poor adherence to protocol,
- Other findings that could lead to the study not meeting its objectives.

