9.5. Medical Emergencies

If a participant experiences a medical emergency during the Study Day 1 visit, the Lead Therapist/Investigator (a licensed physician) will manage the participant during the emergency.

In the event a psychological crisis arises during the study, participants will be instructed to call the Participant Hotline as soon as possible. This call will be routed to the Investigator if it is confirmed that there is indeed a crisis. The Investigator (or a qualified designee) will be on call at all times to receive information from the Participant Hotline.

Upon learning about the psychological crisis, the Investigator will assess the AE by:

- Obtaining a detailed history of the event over the phone
- Collecting information on any concomitant medications
- Assessing expectedness, seriousness, severity, and relationship to the study drug
 - All AEs will be assessed regardless of whether they occurred prior to or after self-administration; however, only those events that occur after study drug administration can be attributed to the investigational product.

If the participant requires immediate care, s/he will be referred to the emergency department of the closest hospital. The emergency department and/or hospital staff, the participant's primary care provider, and/or the Investigator may prescribe medications or take steps to stabilize the participant and to help ameliorate and/or resolve the AE.

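### The working-day alternative in section 10.4 lets an SAE learned of on a Friday reach the Investigator about three days later, so the 24-hour limit does not bind over a weekend

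*Protocol*

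**What the plan says.** Protocol section 10.4 covers all SAEs during the trial, related or not. They must reach the Investigator "within 24 hours (or at the latest on the following working day"), counted from "any member of the study site staff learning that an event occurred, irrespective of causality". The same section starts the time frame for reporting to regulatory authorities when the Investigator first has information about the event. It also asks employees and contractors who discover a serious event to alert site staff, with no time limit for that step.

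Section 9.4 lists the events that pause the study. One rule begins "One participant experiences any of the following during the treatment phase of the trial" and runs from dosing to Day 30 / End-of-Treatment. Its triggers are:

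- "A CTCAE Grade 3 – 5 toxicity which is possibly or probably related to study treatment"
- a suicide attempt
- a confirmed QT finding
- "A serious episode of psychosis as determined by the Investigator that requires immediate medical attention"
- "A severe, non-serious, AE possibly related to study treatment"

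A separate rule pauses the study when two participants have SAEs possibly or probably related to treatment. Section 9.4 does not say how soon a pause must follow the event.

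Section 9.5 says that the Investigator or a qualified designee "will be on call at all times to receive information from the Participant Hotline". The synopsis gives one trial site.

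**The concern.** Two limits are attached to one duty, and the words introducing the second make it the last permissible moment. When the next day is a working day, the two nearly coincide. Before a weekend or holiday they separate, and staff who wait for the next working day comply with the protocol.

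Three things are at stake. First, relatedness is judged by the Investigator (section 10), and a serious psychotic episode counts towards a pause only once the Investigator has determined it. Neither judgement can be made on an event the Investigator has not heard of. Second, the regulatory clock starts at the Investigator's awareness, so time lost earlier comes before that clock and is not counted in it. Third, the looser limit serves no evident purpose at a single site where someone is already on call at all hours.

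**Working it through.** The plan states a time limit, not a statistical quantity, so the check is elapsed calendar time.

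**Inputs**
- The clock starts when any member of site staff learns of the event (section 10.4).
- Outer limit: the following working day (section 10.4).
- Assumption: the working week is Monday to Friday. The protocol does not define it.
- Assumption: section 10.4 gives no clock time for the deadline, so three readings are shown: 09:00, 17:00 and midnight at the end of that day.

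**Formula:** permitted delay = deadline on the next working day minus the time staff learned of the event.

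| Staff learn of the event | Next working day | By 09:00 | By 17:00 | By midnight |
|---|---|---|---|---|
| Monday 09:00 | Tuesday | 24 h | 32 h | 39 h |
| Friday 00:00 | Monday | 81 h | 89 h | 96 h |
| Friday 09:00 | Monday | 72 h | 80 h | 87 h |
| Friday 17:00 | Monday | 64 h | 72 h | 79 h |
| Saturday 09:00 | Monday | 48 h | 56 h | 63 h |
| Friday 09:00, Monday a holiday | Tuesday | 96 h | 104 h | 111 h |
| Friday 17:00, Monday a holiday | Tuesday | 88 h | 96 h | 103 h |

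At the same clock time, Friday to Monday is 3 × 24 = 72 h. For events learned of between the start of Friday and 17:00, the three readings span 64 to 96 h without a holiday. Without the working-day alternative, the maximum is 24 h on every day of the week.

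**Which pause triggers can be affected**
- The two-participant rule is defined on related SAEs, so every event that counts towards it falls under section 10.4.
- Some one-participant triggers would normally also be SAEs under section 10.2: Grade 5 and most Grade 4 toxicities, many suicide attempts, and psychosis needing immediate attention.
- Others need not be SAEs: the severe non-serious event by definition, a QT finding, and a Grade 3 toxicity that meets no seriousness criterion. For these, the section 10.4 limit is not the relevant one.

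**Where the gap remains.** At the Day 4 virtual visit (section 7.1.6), a staff member told of a concerning or serious event directs the participant to appropriate care. That section does not mention telling the Investigator, so section 10.4 supplies the only time limit. If dosing falls on a Tuesday or Wednesday (dosing days are not stated), Day 4 is a Friday or Saturday, when the permitted delay is longest.

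**The case against.** The strongest reply is that the Investigator will usually know already. Section 10.2 has the Investigator or a designee decide whether an event is serious. On Day 1 a physician is on site or within 10 minutes (section 7.1.4), and section 9.5 has the Lead Therapist/Investigator manage medical emergencies. After discharge, confirmed psychological crises are routed from the hotline to the Investigator. This stands for dosing-day events and for crises that participants phone in. It does not reach SAEs, particularly non-psychiatric ones, that staff learn of off-site in another way. A designee's or staff member's knowledge is also not the Investigator's, and section 9.5 sets no limit for staff to pass on SAEs in general.

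A second reply is that the sentence sets a 24-hour standard with a backstop. That is a fair reading of its intent, but the backstop is still what a site can be held to.

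Three stronger readings may tempt a reader, and the protocol supports none of them:

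- **The one-participant pause depends on the SAE report.** No text makes a pause conditional on that report. The triggers are worded as what a participant experiences and are not defined by SAE status. The only SAE-defined pause needs two participants.
- **Up to 8 more people would be dosed in the gap.** Section 4.1 allows up to 8 to be treated together, but no session calendar is given. A site dosing on a Saturday might treat it as a working day. A session also brings together staff and a lead monitor, which makes an unreported event less likely to stay unknown.
- **Two days in seven, about 29% of events, have a limit above 24 hours.** That holds only for a same-clock-time deadline and events spread evenly over the week. Under a 17:00 deadline, an event learned of on Monday at 09:00 already has 32 h. The protocol gives no basis for even spread, and acute events may well cluster around supervised dosing.

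**Conclusion.** The point holds in a limited form. The working-day alternative makes the 24-hour limit non-binding before a weekend or holiday. Given a Monday-to-Friday week, the permitted delay from a Friday is about 64 to 96 hours, and the start of the regulatory clock can move with it. Assessment of events that feed section 9.4 can be delayed: those under the two-participant related-SAE rule, and those one-participant triggers that are also SAEs. How often this would happen cannot be estimated from the protocol. The other routes to the Investigator keep the practical gap small. It is a worthwhile tightening of safety oversight, but it does not show that the pause rules fail.

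**What to change.** In section 10.4, delete the bracketed working-day alternative so that the limit is 24 hours on any day of the week. Name the existing on-call arrangement in section 9.5 as the route for staff to report SAEs, since that section now describes it only for the hotline and psychological crises. Reconcile section 10.4 with section 9.4, so that it is clear how a reported event reaches assessment against the pause rules; the rules themselves need not change for this.

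The cost is one deleted clause, a cross-reference, and an occasional weekend call to an Investigator or designee who is already on call.
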